6 CONSENT

We believe need for individual patient or personal/legal rep consent should be waived. The following aspects, needed for seeking informed consent to access patients' records, are considered disproportionate to this observational study: the difficulty, or even impossibility, of locating and contacting all patients; the high costs and effort needed; the risk of bias (Al-Shahi et al., 2005; McKinney et al., 2005; Jousilahti et al., 2005); and the very low risk of breaching individuals' privacy. In addition, strict and thorough strategies will be put in place data protection and confidentiality. Moreover, the British public has been found to be highly supportive of the use of personal medical data in non-commercial medical research which "has no effect on the individuals being studied and has been approved by an accredited research ethics committee" (Peto et al., 2004, p. 1030). Therefore, consent will not sought.

ELIGIBILITY CRITERIA

7.1 Inclusion Criteria

- Over 16 years old- 65 years old
- On cardiac monitoring (PiCCO device)

7.2 Exclusion Criteria

EXCLUSION CRITERIA

Full title of the research: **The impact of systemic pH on cardiac function and clinical outcome in the critically ill patient.**

IRAS Project ID: **227870**

- **Atrial or ventricular arrhythmia:** you need a stable pulse to measure the contour.
- **Aortic, mitral or tricuspid valve insufficiency.** In the case of valve insufficiency the valve does not close correctly. Therefore, the thermodilution curve is affected by indicator regurgitation, resulting in a prolonged indicator decay time.
- **Intra-Aortic Balloon pump:** once again, the pulse contour is all wrong; but you can still get thermodilution cardiac output measurements.
- **Aortic aneurysm:** the contour will be bizarre because the arterial compliance is going to be weird, with the aortic aneurysm acting as a damping system by absorbing all the pressure wave.
- **Extracorporeal circuit:** when you are on bypass, there is no real arterial waveform
- **Pneumonectomy:** PiCCO relies on there being a relatively normal pulmonary vasculature.
- **Massive pulmonary embolism:** as above; it is essentially a pneumonectomy by embolism.
- **Intracardiac shunt:** the PA catheter will also give an inaccurate thermodilution reading.
- **Less than a minimal tidal volume 6-8mL/kg**
- **NON-positive pressure ventilated patients:**
 - **Why does Stroke Volume Variation only apply to positive pressure ventilated patients?** It still applies in spontaneously breathing patients; however it is a poorer predictor of fluid responsiveness.
 - **Why? The sensitivity is decreased: its only 63%.** The spontaneous breathing efforts draw a smaller tidal volume, and from such minor changes in thoracic pressure there would insufficient change in ventricle loading; so there may still be changes to stroke volume, but they would be tiny and difficult to measure.
 - **- If there is profound hypovolemia, the IVC can collapse on inspiration.** Obviously this decreases preload, and confuses your SVV. You cannot predict fluid responsiveness this way, because you never get an accurate impression of preload.
 - **- In spontaneous respiration, inspiration increases the right ventricular preload,** which means the right ventricular filling is likely still appear adequate even if there is some hypovolemia. In spite of low overall volume, the right ventricular preload remains adequate, and thus at least one of the ventricles is likely to be

Full title of the research: **The impact of systemic pH on cardiac function and clinical outcome in the critically ill patient.**

IRAS Project ID: **227870**

operating in the preload-independent straight part of the Frank-Starling curve

- **Severe obesity:** In obese patients, Extravascular Lung Water Index (EVLWI) is underestimated because it is related to the body weight.

7 RECRUITMENT

The recruitment section may include:

- Method for identifying and recruiting participants for the study: mechanical screening. It will be done daily by researcher in each ICU. Those patient on cardiac monitoring (PiCCO device).
- Who will identify and approach participants for consent: Not needed

8 STATISTICAL METHODS

The description of quantitative variables is carried out with central tendency and dispersion indices, whether based on values (mean and standard deviation) or on ordinations (median and interquartile range) according to whether they meet normality or not, respectively. Its graphic representation is done with Histograms and Cash Diagrams. The description of categorical variables is performed with absolute and relative frequencies in percentages. Its graphic representation is done with bar charts.

The relationship between categorical variables is analyzed by comparing proportions with the Pearson Chi-square test, provided that there are less than 20% of squares in the contingency table with expected frequencies less than 5. In the case that there is more 20% of squares with expected frequencies less than 5, the Fisher's exact test is used bilaterally.

Full title of the research: **The impact of systemic pH on cardiac function and clinical outcome in the critically ill patient.**

IRAS Project ID: **227870**

The magnitude of the effect of the relationship between two binary variables has been analyzed with the Ratios of proportions or Relative Risk and with the Odds Ratio.

The relationship between a binary exposure variable and a quantitative response is analyzed with the Student-Fisher t test for independent samples if the normality condition is met. According to whether or not the equality of variances are met, the Student-Fisher t test is used for independent groups for homogeneous variances or for non-homogeneous variances, respectively. In case of not fulfilling the condition of normality, the comparison of two means is made with the non-parametric Mann-Whitney U test.

The comparison between a polytomic predictor and a quantitative response is made through the analysis of variance (ANOVA) in the case of meeting the conditions of normality and homogeneity of variances. If any of these conditions is not met, it is done with the non-parametric H test of Kruskal-Wallis. If the polytomic predictor is ordinal, the ANOVA trend test or the non-parametric Jonckheere-Terpstra trend test is also used, depending on whether normality is met or not, respectively.

The relationship between two independent quantitative variables is evaluated with the correlation coefficient r of Pearson if normality is met, or with the nonparametric correlation coefficient ρ of Spearman if normality is not met. Its graphic representation is made with the scatter diagrams or points.

Full title of the research: **The impact of systemic pH on cardiac function and clinical outcome in the critically ill patient.**

IRAS Project ID: **227870**

Normality is assessed with the Kolmogorov-Smirnov test with the Lilliefors significance correction for large samples, or with the Shapiro-Wilks test for small samples. The equality of variances is analyzed with the Levene variance homogeneity test.

The relationship between two related quantitative variables is performed using the Student-Fisher t-test for related samples in case the normality condition is met. Otherwise, the non-parametric Wilcoxon T test is used. The relationship between two paired categorical variables is performed by the McNemar symmetry test.

The relationship between a continuous quantitative response and one or several predictors, whether binary, polytomic or quantitative, is done with Simple or Multiple Linear Regression respectively.

The polytomous predictors variables are introduced in the Linear Regression models broken down into binary indicator variables coded with respect to the first reference category.

An estimative multivariate linear regression model of the effect of the predictor Change of pH (between the lowest and highest pH) on the response Change in cardiac output (corresponding to the moments between the lowest and the highest pH) has been performed. The possible role as confounding factors of several variables on this relationship has been evaluated. A predictive multivariate model of linear regression has been performed to evaluate the factors that intervene in the Cardiac Contractility.

Full title of the research: **The impact of systemic pH on cardiac function and clinical outcome in the critically ill patient.**

IRAS Project ID: **227870**

Both the predictive and the estimative models have been carried out with the manual backward step procedure using the criterion of decreasing statistical significance to establish the order to evaluate the withdrawal or permanence of each predictor.

In the multivariate predictive linear regression model, the criterion of statistical significance was used to decide the maintenance or withdrawal of the predictors in each step. They remain in the model if they are significant and are removed from the model if they are not significant.

In the multivariate models of linear regression, the criterion of clinical significance has been used to decide on the maintenance or withdrawal of the predictors in each step. They remain in the model if they produce a change greater than 10% in the coefficient of the predictor of interest (presence of confounding bias) and withdraw if the change is less than 10% (absence of confounding bias).

The conditions of application of the simple or multiple linear regression (linearity, independence, normality and equality of variances) are evaluated by analysing the residuals.

Values of $P < 0.05$ are considered significant. The statistical treatment has been performed the statistical package SPSS, version 18 (SPSS Inc, Chicago, IL, USA).

Full title of the research: **The impact of systemic pH on cardiac function and clinical outcome in the critically ill patient.**

IRAS Project ID: **227870**

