2 BACKGROUND AND RATIONALE

3 OBJECTIVES

Goals

Primary

1. Assess whether there are significant changes in cardiac function associated with changes in blood pH.
2. Relate the changes in cardiac function to presence or absence of underlying cardiac disease.

Secondary

3. To establish which factors affected by blood pH have an impact on cardiac function.

Full title of the research: **The impact of systemic pH on cardiac function and clinical outcome in the critically ill patient.**

IRAS Project ID: **227870**

4. Study the mortality of patients admitted to the Intensive Care Unit (ICU) who had continuous cardiac monitoring at any time during their admission and relate it to changes in blood pH.

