4 STUDY DESIGN

- Study population and groups: those patients on haemodynamic monitoring in ICU (PiCCO monitoring)
- **Calculation of the sample size:**

Taking into account that the primary objective of the study is to analyze the relationship between the quantitative variables: change in pH and change in Cardiac Contractility, assuming an alpha risk of 5% (95% confidence level), a 20% beta risk (power of 80%) and a minimum ratio that has an estimated clinical significance with a correlation coefficient of 1.5, a bilateral estimate of sample size of 346 subjects is obtained. Assuming a 5% loss (17 individuals) during the study a total of 363 cases would be necessary.

- **Statistical methods:**

The description of quantitative variables is carried out with central tendency and dispersion indices, whether based on values (mean and standard deviation) or on ordinations (median and interquartile range) according to whether they meet normality or not, respectively. Its graphic representation is done with Histograms and Cash Diagrams. The description of categorical variables is performed with absolute and relative frequencies in percentages. Its graphic representation is done with bar charts.

Full title of the research: **The impact of systemic pH on cardiac function and clinical outcome in the critically ill patient.**

IRAS Project ID: **227870**

The relationship between categorical variables is analyzed by comparing proportions with the Pearson Chi-square test, provided that there are less than 20% of squares in the contingency table with expected frequencies less than 5. In the case that there is more 20% of squares with expected frequencies less than 5, the Fisher's exact test is used bilaterally.

The magnitude of the effect of the relationship between two binary variables has been analyzed with the Ratios of proportions or Relative Risk and with the Odds Ratio.

The relationship between a binary exposure variable and a quantitative response is analyzed with the Student-Fisher t test for independent samples if the normality condition is met. According to whether or not the equality of variances are met, the Student-Fisher t test is used for independent groups for homogeneous variances or for non-homogeneous variances, respectively. In case of not fulfilling the condition of normality, the comparison of two means is made with the non-parametric Mann-Whitney U test.

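### Choosing the two-group t test by a Levene pre-test can move the procedure's error rate off 5% when group sizes are very unequal and SDs differ moderately; using Welch throughout avoids this

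*Combined protocol and SAP*

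**What the plan says.** Section 8 (Statistical Methods) sets a general rule for a binary exposure and a quantitative response. If normality is met, a t test is used, and its version depends on the variances: "According to whether or not the equality of variances are met, the Student-Fisher t test is used for independent groups for homogeneous variances", or the non-homogeneous version otherwise. If normality is not met, the Mann-Whitney test is used. The judging test is named a little later: "The equality of variances is analyzed with the Levene variance homogeneity test". Values of P below 0.05 "are considered significant. The statistical treatment has been performed the statistical package SPSS, version 18". No separate level is given for Levene's test, and nothing allows for the two-stage choice. The same text stands in section 4 (Study Design) and in the study summary.

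One place where the rule might be used is the second primary goal in section 3: "Relate the changes in cardiac function to presence or absence of underlying cardiac disease". Section 8 does not say which method serves that goal.

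On size, section 4 states that "a bilateral estimate of sample size of 346 subjects is obtained". It gives no expected split into groups and no SDs.

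**The concern.** A non-significant Levene test does not show that variances are equal. When one group is small the test has limited power against moderate differences, so the pooled t test is often kept where its standard error is wrong. With unequal group sizes that matters. If the smaller group is the more variable one, the pooled standard error is too small and false positives rise. If it is the less variable one, the standard error is too large and the test becomes strict. Switching to the unequal-variance test only after Levene rejects repairs this in part.

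At stake is whether a two-group result reported at P<0.05 carries a 5% error rate. The correlation between change in pH and change in contractility, and the sample size built on it, are not affected.

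**Working it through.** **Inputs from the plan.** Levene, then the pooled or unequal-variance t test; two-sided 0.05; 346 evaluable patients.

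**The plan's own figure.** n = ((1.960 + 0.842)/atanh(r))² + 3. With r = 0.15, atanh(r) = 0.1511 and n = 346.6, which matches 346. The correlation is printed as 1.5, which is not a possible value; 0.15 reproduces the total. With losses, 346 × 1.05 = 363.3, the stated 363. So 346 is the right size for the check.

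**Assumptions, because the plan is silent.** Small group of 20 to 173 patients (6% to 50%); SD ratio r (small group to large group) of 0.7 to 2.0; mean-centred Levene at 0.05; normal data; no true difference in means.

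**Why the pooled test errs.** Set the large group's SD to 1.
- True variance of the mean difference: V = r²/n₁ + 1/n₂
- What the pooled test estimates: P = [((n₁−1)r² + n₂−1)/344] × (1/n₁ + 1/n₂)
- Approximate error rate: 2[1 − Φ(1.967 × √(P/V))]

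For n₁ = 20, n₂ = 326:
- r = 1.3: V = 1.69/20 + 1/326 = 0.0876; P = 1.038 × 0.0531 = 0.0551; √(P/V) = 0.793; error about 11.9%.
- r = 0.8: V = 0.64/20 + 1/326 = 0.0351; P = 0.980 × 0.0531 = 0.0520; √(P/V) = 1.218; error about 1.7%.

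With 173 per group, P = V and the pooled test is correct.

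**Simulation, group of 20 of 346 (60,000 runs per row).**

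| SD ratio | Levene rejects | Pooled always | Levene then t | Welch always |
|---|---|---|---|---|
| 0.7 | 44.9% | 0.7% | 3.9% | 5.0% |
| 0.8 | 20.3% | 1.7% | 3.4% | 5.0% |
| 1.2 | 20.1% | 9.4% | 7.9% | 5.0% |
| 1.3 | 34.9% | 12.1% | 8.7% | 5.1% |
| 1.4 | 51.4% | 14.2% | 8.2% | 4.8% |
| 1.5 | 65.6% | 17.0% | 8.1% | 5.1% |

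The pooled column agrees with the formula. At r = 1.3 Levene misses the difference in about 65% of studies, and the pooled test is significant in 12.2% of those: 0.65 × 12.2% = 7.9 of the 8.7 points. At r = 1.0 and r = 2.0 the two-stage procedure is close to nominal (5.2% and 5.1%). The drift therefore belongs to moderate differences.

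**Range over SD ratios 0.7 to 2.0, by group size (20,000 runs per cell).**

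| Small group | Share of 346 | Levene then t |
|---|---|---|
| 20 | 6% | 3.4% to 8.9% |
| 35 | 10% | 3.8% to 7.3% |
| 70 | 20% | 3.9% to 6.3% |
| 104 | 30% | 4.3% to 5.4% |
| 173 | 50% | about 5% |

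Welch in every case gives 4.7% to 5.4%. The simulation standard error is about √(0.05 × 0.95/20,000) = 0.15 points, so the last tenth should not be pressed. With 363 patients a group of 20 gives 3.4% to 8.8%. Adding the plan's normality step (6,000 runs, group of 20) gives 3.3% at r = 0.8 and 8.8% at r = 1.3, so leaving that step out does not create the result.

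**The case against.** The strongest objection is that nothing in the documents puts a t test and a very small group together. Section 8 assigns no t test to the cardiac-disease goal, and it provides multiple linear regression with binary predictors, which could serve instead. The size of the group is also unclear. The Introduction says patients with a cardiac history are excluded, which would leave the group empty or nearly so. Section 7.2 has no general exclusion of that kind, and the data form under section 20 records ischaemic heart disease, heart failure, cardiogenic shock and cardiothoracic surgery, so the group could be sizeable. Neither reading yields 6%. This objection stands, and it limits the point to a conditional one.

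A reader might also infer that the P<0.05 threshold fails outright, or that it is too liberal because cardiac patients are more variable. The documents support neither. The drift nearly vanishes at a 30% share, is absent with equal groups, and is small at large SD ratios. No SDs are given, so even its direction is unknown. Nor do the ranges describe the pooled test alone, which drifts much further (0.7% to 17.0% in the group-of-20 table).

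Finally, Levene-then-choose is a conventional rule, and the plan already holds the unequal-variance test in reserve. That is fair: this is neither a contradiction nor a missing method. It remains a rule that can be improved at almost no cost.

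**Conclusion.** The point holds in conditional form and is minor. The two-group rule does not secure its stated 5% level when group sizes are very unequal and SDs differ moderately. The departure is about 3.4% to 8.9% at a 6% share, narrows to 3.9% to 6.3% at 20%, and is negligible from about 30% upward. These figures rest on assumed shares, SD ratios and normal data.

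The rule covers any two-group comparison of a quantitative variable. Whether it reaches the second primary goal depends on the method chosen for that goal and on reconciling the Introduction with section 3 and the data form. That conflict comes first, since it decides whether the comparison exists.

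**What to change.** In sections 4 and 8 and in the study summary, delete the Levene step for two-group comparisons. State that the unequal-variance (Welch) t test is always used and reported with its confidence interval. This takes one sentence in each place and uses a test already in the plan.

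The cost is some power if the variances are in fact equal: about 3 points for a group of 20 (77% against 80% for the pooled test), 1 to 2 points for 35, and under 1 point for 70 or more.

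Separately, state which method answers the cardiac-disease goal, and reconcile the passages on whether patients with a cardiac history are enrolled.

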IRAS Project ID: **227870**

11. [name] (SpR Anaesthesia)

12. [name] (ICU Clinical Fellow)

STUDY SUMMARY

STUDY OVERVIEW	
Full title	The impact of systemic pH on cardiac function and clinical outcome in the critically ill patient
Objectives	Hypothesis Titration studies in animals with normal cardiac function show that a reduction in blood pH (and presumably that of the intracellular and interstitial compartments) from the normal level of 7.40 to 7.20 is associated with a rise in cardiac output. However, when blood pH is less than 7.20, cardiac output is reduced. Similar studies in humans with or without normal cardiac function have not been done, and yet blood pH at which aggressive treatment is recommended has been set at 7.20 based solely on animal experiments. We hypothesize that a change in blood pH in humans will also affect cardiac function, but the level of blood pH at which this is observed might be similar or different in humans. In addition, the presence or absence of

Full title of the research: **The impact of systemic pH on cardiac function and clinical outcome in the critically ill patient.**

IRAS Project ID: **227870**

	
underlying cardiac disease and the type of acid-base abnormality present might modify the response of the heart to changes in blood pH.
 
Goals
 
Primary
 
 1. Assess whether there are significant changes in cardiac function associated with changes in blood pH. 2. Relate the changes in cardiac function to presence or absence of underlying cardiac disease. 
Secondary
 
 3. To establish which factors affected by blood pH have an impact on cardiac function. 4. Study the mortality of patients admitted to the Intensive Care Unit (ICU) who had continuous cardiac monitoring at any time during their admission and relate it to changes in blood pH.
Type of trial	It is not a trial
Trial design and methods	It is not a trial
Health condition(s) or problem(s) studied	It is not a trial
Target sample size	Taking into account that the primary objective of the study is to

Full title of the research: **The impact of systemic pH on cardiac function and clinical outcome in the critically ill patient.**

IRAS Project ID: **227870**

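### With three or more groups, normal data with unequal variances are sent to Kruskal-Wallis, which does not correct for unequal spread; the plan's own two-group rule for normal data uses an unequal-variance test

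*Combined protocol and SAP*

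**What the plan says.** Section 8 (Statistical Methods) chooses tests by type of variable. The same text stands in the Study Summary and in Section 4 (Study Design).

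- **Three or more categories, quantitative response.** ANOVA is used "in the case of meeting the conditions of normality and homogeneity of variances". The fallback is: "If any of these conditions is not met, it is done with the non-parametric H test of Kruskal-Wallis". Failure of either condition is enough.
- **Two groups, normal data.** "the Student-Fisher t test is used for independent groups for homogeneous variances or for non-homogeneous variances, respectively". This branch has a version for unequal variances.
- **Two groups, non-normal data.** "In case of not fulfilling the condition of normality, the comparison of two means is made with the non-parametric Mann-Whitney U test". No variance condition applies here.
- **Variance check.** "The equality of variances is analyzed with the Levene variance homogeneity test".
- **Level.** "Values of $P < 0.05$ are considered significant".

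No variance-robust test for three or more groups, such as Welch's ANOVA, is named.

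**The concern.** Non-normality and unequal variance are different problems, and the multi-group rule treats them with one remedy. Kruskal-Wallis relaxes normality. Its null distribution, however, is derived for groups that share one distribution, spread included. If a small group is much more variable than the rest, its mean rank fluctuates more than the statistic allows for, and the test rejects too often when the means are equal. If the largest group is the most variable, it rejects too rarely.

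The plan recognises the problem for two groups of normal data and handles it suitably, but does not carry that choice over to three or more. What is at stake is whether a multi-group comparison reported at the 5% level has that level as a comparison of means.

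**Working it through.** **Inputs from the documents.** Level 0.05 (Section 8). Evaluable sample 346 (Section 4). Sequence: Levene's test, then ANOVA or Kruskal-Wallis (Section 8).

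**Inputs assumed.** The documents give no group sizes or SDs for any predictor with several categories. The range taken is three or five groups totalling 346, from near-equal to 246/60/40, with a largest-to-smallest SD ratio of 1 to 4, normal data and equal means.

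**The plan's own figures.** The 346 comes from the correlation calculation n = ((z0.975 + z0.80)/atanh(r))² + 3. With r = 0.15 this is (2.802/0.1511)² + 3 = 346.6. The correlation is printed as 1.5, for which the formula has no value, so 0.15 is assumed. Nothing below depends on this beyond the total of 346. The nominal 5% is reproduced when SDs are equal (first and sixth rows of the table).

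**Formulas.**
- Kruskal-Wallis: H = 12/(N(N+1)) · Σ Rᵢ²/nᵢ − 3(N+1), with Rᵢ the rank sum of group i, referred to chi-square on k−1 degrees of freedom.
- Welch: wᵢ = nᵢ/sᵢ², W = Σwᵢ, m̃ = Σwᵢmᵢ/W, L = Σ(1−wᵢ/W)²/(nᵢ−1). Then F = [Σwᵢ(mᵢ−m̃)²/(k−1)] / [1 + 2(k−2)L/(k²−1)] on k−1 and (k²−1)/(3L) degrees of freedom.

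**Simulation.** 40,000 data sets per row. The Monte Carlo standard error at 5% is √(0.05 × 0.95/40,000) = 0.11 percentage points. Entries are the percentage rejected at 0.05.

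| Group sizes | SDs | Kruskal-Wallis | Classical ANOVA | Welch |
|---|---|---|---|---|
| 115/115/116 | 1/1/1 | 4.9 | 5.0 | 5.0 |
| 115/115/116 | 1/1.5/2 | 5.4 | 5.4 | 4.9 |
| 115/115/116 | 1/2/3 | 6.0 | 6.1 | 5.0 |
| 115/115/116 | 1/1/3 | 6.7 | 7.0 | 5.1 |
| 115/115/116 | 1/2/4 | 6.6 | 6.7 | 5.1 |
| 246/60/40 | 1/1/1 | 5.0 | 5.1 | 5.0 |
| 246/60/40 | 1/1.5/2 | 11.2 | 19.1 | 5.1 |
| 246/60/40 | 1/2/3 | 14.6 | 27.1 | 4.9 |
| 246/60/40 | 3/2/1 | 1.3 | 0.5 | 4.8 |
| 246/60/40 | 3/1/1 | 0.7 | 0.1 | 4.9 |
| 200/100/46 | 1/1.5/2 | 9.4 | 14.7 | 4.8 |
| 200/100/46 | 1/2/3 | 12.3 | 20.0 | 5.0 |
| 200/100/46 | 3/2/1 | 2.1 | 1.2 | 4.9 |
| 140/80/60/40/26 | 1/1.5/2/2.5/3 | 12.0 | 21.1 | 5.0 |
| 140/80/60/40/26 | 3/2.5/2/1.5/1 | 2.2 | 1.5 | 4.9 |
| 70/69/69/69/69 | 1/1.5/2/2.5/3 | 5.7 | 6.3 | 4.8 |

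For 200/100/46 with SDs 1/1.5/2, repeat runs of 20,000 and 8,000 data sets gave 9.4% and 9.6% for Kruskal-Wallis and 4.9% and 5.0% for Welch. Milder differences at the same sizes matter less: SDs 1/1.25/1.5 gave 7.5%, and 1/1.1/1.2 gave 5.9%.

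**Does the plan's rule really end at Kruskal-Wallis?** Yes. Levene's test rejected in 99% to 100% of the data sets with unequal SDs, and the two-stage rule (Levene, then ANOVA or Kruskal-Wallis) gave practically the same rejection rates as Kruskal-Wallis alone. The normality test was not simulated, but a failure there leads to Kruskal-Wallis too.

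**The case against.** The best defence is that no planned analysis is shown to use this rule. Section 8 is a generic list. The main question is handled by correlation and by linear regression of change in cardiac output on change in pH. The second primary goal, presence or absence of cardiac disease, is binary. No objective in Section 3 compares three or more groups. This stands, and it limits the importance of the point.

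A reader might infer that comparisons by acid-base disorder or by admitting diagnosis will be declared significant at more than twice 5%. The documents do not support that. The hypothesis says "the type of acid-base abnormality present might modify the response of the heart to changes in blood pH", which is effect modification. That calls for an interaction with pH change, and no one-way test addresses it, Welch's included. Admitting diagnosis is only a field on the data collection form printed under Section 20, with no stated analysis, and Section 8 also allows such factors into regression as indicator variables. The rule could still be applied to it. The form lists 11 main categories, so 346 patients average about 31 each (346/11 = 31.5), and equal sizes are unlikely.

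Three further limits stand:
- The size depends on assumed imbalance and spread, and near-balanced groups show little inflation.
- When small groups are the more variable, Kruskal-Wallis is closer to 5% than the classical ANOVA it replaces (14.6% against 27.1% at 246/60/40 with SDs 1/2/3). The switch improves matters there without curing them.
- The contrast with the two-group rule holds for normal data only. The Mann-Whitney branch has the same weakness under unequal spread.

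**Conclusion.** The point holds as a desirable refinement of a secondary rule. As written, normal data with unequal variances across three or more groups go to a test that does not hold 5% for equality of means. Under the assumed group sizes and SDs its actual level runs from about 1% (largest group most variable) to about 15% (smallest group most variable), and is 5.4% to 6.7% for near-equal groups. Welch's ANOVA stays at 4.8% to 5.1% throughout.

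Two stronger conclusions are not supported. The primary correlation and regression and the sample size are untouched. And because only normal data were simulated, the results do not justify making Welch's ANOVA the default everywhere or dropping Kruskal-Wallis for non-normal data.

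**What to change.** Split the fallback in the multi-group rule. If the data are normal within categories but Levene's test rejects, use Welch's ANOVA, with Games-Howell for pairwise comparisons. If normality fails, keep Kruskal-Wallis, and state that when spreads differ it compares distributions and not means. This extends to three or more groups the choice already made for two groups of normal data.

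The cost is one sentence in each of three places (Study Summary, Section 4, Section 8). No new data and no change in sample size are needed.
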